Continuous and normally distributed variables were expressed as mean with a standard difference (SD) and compared using Student's t-test, while non-normally distributed variables were presented as median with interquartile range (IQR) and compared using the non-parametric Mann–Whitney U test. Categorical variables were expressed as numbers and percentages and tested by Fisher's exact test or the χ^2 test.

Overall survival (OS) was defined as the time interval between initial TACE or LR and all-cause death. Patients who survived up to the last follow-up date (October 15th, 2021) or were lost to follow-up were censored. Survival curves were displayed using the Kaplan–Meier (K-M) method and compared with the log-rank test.

Python software was applied for train AI models and detailed codes were uploaded as supplements (<https://github.com/ApocalypseZ/Survival>). R software and related packages (survival, rms, reportROC, survminer, and ggplot2) were adopted to conduct statistical analysis and plot figures. $P < 0.05$ was considered statistically significant.

Results information for studies

Basic clinical characteristics

In this multicenter study, 4991 patients met the selection criteria and were included. Of these, 1916 patients (38.39%) were amenable to LR while 3075 patients (61.61%) submitted to TACE (Figure 1). 4192 (84%) and 799 (16%) patients were divided into train and validation sets, respectively. Among train set, 1622 (38.7%) were underwent LR while 2570 (61.3%) adopted TACE treatment. In validation set, 294 (36.8%) and 505 (63.2%) were allocated to LR and TACE treatment, respectively. The demographic and clinicopathological characteristics of the cohort are shown in Table 1. The variables associated to tumor burden were lower in the LR group than those of the TACE group in overall cohort: (a) The largest tumor diameters were smaller in the

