LR group (4.60 [3.00;7.00] cm) than in the TACE group (6.30 [4.00;9.90] cm); (b) The tumor lesions of HCC were relatively few in the LR group (1.0 [1.0-1.0] lesion) than in the TACE group (1.0 [1.0-2.0] lesions). In addition, the liver function of HCC patients (CPS and Child-Pugh stage) varied remarkably between the LR and TACE groups. A higher proportion of Child stage B patients were included in the TACE group (17.6%) than in the LR group (11.1%). The median follow-up was 54.0 months (IQR 38.7–69.2 months) for LR therapy and 36.1 months (IQR 24.7–54.7 months) for TACE. The 1-year, 3-year, and 5-year survival probability was 91.7%, 79.6%, and 70.8% for LR allocation, respectively, while 74.8%, 41.5%, and 26.4% for TACE treatment, respectively. Although there were significant differences between the LR and TACE groups, we perceived therapy type as a pivotal factor in the AI models to simulate a real-world clinical setting, considering the precise prediction of AI technologies.

Selection of the optimal AI model

We applied 10 kinds of machine learning survival algorithms in the train cohort, of which seven AI models performed well, with the C-index > 0.7 , and were retained: (i) random survival forest (RSF), (ii) conditional survival forest, (iii) DeepSurv algorithm, (iv) Extra Survival Trees, (v) Gompertz, (vi) standard Cox proportional hazards model (CoxPH), and (vii) PTA model based on the above six models. For model estimation, the C-index and IBS of these seven AI models were displayed in the Table 2. The C-index of the PTA model was 0.854 and 0.801 in the train and validation cohorts, respectively, which were higher than other six AI models except for the RSF model in train cohort. Even though the RSF model achieved the highest C-index (0.926) in the train set, while in the validation cohort, the C-index was only 0.765, indicating the potential presence of over-fitting in the RSF model. Given the C-index of the train and validation cohorts, the PTA model derived from the above six algorithms outperformed other single-algorithm models. As expected, the IBS of the six single algorithms and PTA algorithm was far smaller than 0.25, demonstrating their capability for clinical application (Supplement 2-3).

Predictive performance of the PTA model

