To further validate the PTA model, we drew the receiver operating characteristic curves (ROC) and calculated the AUC. The AUC values for 1 year, 3 years, and 5 years were 0.912 (95% confidence interval [CI], 0.887–0.938), 0.914 (95% CI, 0.891–0.937), and 0.928 (95% CI, 0.903–0.953), respectively (Supplement 4A-C and Supplement 5). In addition, the AUCs for TACE treatment were 0.893 (95% CI, 0.858–0.928), 0.857 (95% CI, 0.810–0.904), and 0.858 (95% CI, 0.787–0.929), whereas the AUCs for LR were 0.873 (95% CI, 0.805–0.941), 0.850 (95% CI, 0.797–0.903), and 0.839 (95% CI, 0.779–0.899) at 1, 3, and 5 years, respectively (Supplement 5). The full summary of all indicators (accuracy, sensitivity, specificity, positive predictive value [PPV], negative predictive value [NPV], positive likelihood ratio [PLR], and negative likelihood ratio [NLR]) were compiled in Supplement 5. These results suggested that the PTA model could accurately predict HCC survival at the observed follow-up time.

Additionally, the performance and discriminative ability of clinical guidelines (BCLC, BCLC B sub-classification, HKLC, and ITA.LI.CA stage), tumor-burden-based models (up-to-seven model, four-and-seven model, and six-and-twelve model), and models adopting other parameters (HAP score, mHAP II score, mHAP III score, ALBI score, and MESIAH score) were compared with the PTA model (Table 2). As expected, the 1-, 3- and 5-year auROC and C-index of the PTA model were higher than those of the above mentioned models and prognostic scores. Moreover, three calibration curves were plotted to show the predicted probabilities of death caused by HCC in 1, 3, and 5 years (Supplement 4D-F). The observed survival was within a negligible margin of error of the predicted survival, showing that the performance of the PTA model was overwhelmingly good.

Comparison with clinical guidelines

Next, we compared the discriminative performance of the PTA model in selecting potential candidates with that of the BCLC and HKLC guidelines. As stated above,

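### PTA is said to outperform its component models and 12 prognostic systems, but the text plans and gives no paired interval or test for any difference; C-index gaps below about 0.02 may be unresolved

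*Combined protocol and SAP*

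**What the plan says.** Section 3 (Model development) retains a model if its C-index is at least 0.7 and lists the performance measures. It gives no rule for deciding that one model beats another. Section 4 (Model estimation) compares PTA with 12 prognostic systems by estimating auROC and C-index, and says nothing about the uncertainty of a difference.

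Section 6 (Statistical analyses) names t, Mann–Whitney, Fisher and chi-square tests for patient characteristics. For outcomes it says: "Survival curves were displayed using the Kaplan–Meier (K-M) method and compared with the log-rank test". None of these compares two C-indices or two AUCs obtained on the same patients.

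The results then draw two conclusions:

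- Under Selection of the optimal AI model: "the PTA model derived from the above six algorithms outperformed other single-algorithm models". The values printed are "The C-index of the PTA model was 0.854 and 0.801 in the train and validation cohorts, respectively" and, for RSF, "in the validation cohort, the C-index was only 0.765". The same paragraph concedes the training result: "Even though the RSF model achieved the highest C-index (0.926) in the train set".
- Under Predictive performance of the PTA model: "As expected, the 1-, 3- and 5-year auROC and C-index of the PTA model were higher than those of the above mentioned models", with the prognostic scores included in the same sentence.

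The discrimination intervals in the text are for PTA's own AUCs. No C-index has an interval in the text, and no difference has an interval or P value.

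**The concern.** Two models scored on the same patients have correlated C-indices. A rank order therefore says little until the difference has its own interval. This matters most for the six single algorithms, because PTA is built from them and small gaps are plausible.

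The conclusion over RSF also has to rest on the validation set. In the training set RSF is ahead by 0.926 − 0.854 = 0.072, which the authors themselves attribute to possible over-fitting.

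At stake is whether the ensemble's reported advantage in discrimination over its own components is more than sampling variation. PTA is the model put on the public website and used to classify treatment allocations, so the evidence for that advantage should be visible.

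**Working it through.** **No stated figure to reproduce.** The text gives no event count, C-index standard error or precision target. The split is consistent: "4192 (84%) and 799 (16%) patients were divided into train and validation sets, respectively" (4192 + 799 = 4991), and "In validation set, 294 (36.8%) and 505 (63.2%) were allocated to LR and TACE treatment, respectively" (294 + 505 = 799).

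**Number of readings by sign.** The six single algorithms are ranked on C-index: 6. The 12 systems (4 staging systems, 3 tumour-burden models, 5 scores) are compared on C-index and three AUCs: 12 × 4 = 48. Total 6 + 48 = 54. This takes the 12-system comparison to be on validation patients; the text does not name the cohort.

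**Gauge of the standard error.** PTA's 3-year AUC is 0.914 (0.891 to 0.937), so SE = (0.937 − 0.891)/3.92 = 0.0117 and the half-width is 0.023. Stated 3-year survival (79.6% LR, 41.5% TACE) gives 294 × 0.204 + 505 × 0.585 ≈ 355 deaths and 444 survivors among 799. The Hanley–McNeil half-width is then 0.0215, against about 0.009 for the training set or all 4991 patients, so the interval fits the validation set. The match is looser at 1 year (0.0318 calculated, 0.0255 stated) and 5 years (0.0179 calculated, 0.025 stated), where censoring matters.

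A simulation of 294 LR and 505 TACE patients (250 replicates, exponential survival matched to stated 3-year survival, censoring from stated follow-up) gave about 372 deaths and an SE of one C-index of about 0.010 to 0.0125.

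**Paired difference.** SE_diff = SE × √(2(1 − ρ)), where ρ is the correlation between the two C estimates. The 95% interval is 0.036 ± 1.96 × SE_diff. The difference detectable with 80% power is (1.96 + 0.84) × SE_diff. Neither SE nor ρ is in the documents. With SE = 0.0117:

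| ρ | SE_diff | 95% interval for 0.036 | Detectable, 80% power |
|---|---|---|---|
| 0.5 | 0.0117 | 0.013 to 0.059 | 0.033 |
| 0.8 | 0.0074 | 0.021 to 0.051 | 0.021 |
| 0.9 | 0.0052 | 0.026 to 0.046 | 0.015 |
| 0.95 | 0.0037 | 0.029 to 0.043 | 0.010 |

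At ρ = 0.5, z = 0.036/0.0117 = 3.08, above the Bonferroni values for 6 comparisons (2.64) and 18 (2.99). At SE 0.015 and ρ = 0.5 the interval is 0.007 to 0.065. Over the range tried (SE 0.010 to 0.015, ρ 0 to 0.95) the interval reaches zero only at ρ = 0 with SE of 0.013 or more.

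**Simulated power, from loosely to closely correlated scores.**

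- True difference 0.036: SE_diff 0.007 to 0.009, z 3.9 to 5.2, power 97% or more.
- About 0.02: 61% to 97%.
- About 0.01: 19% (score correlation 0.83) to 80% (0.97).
- About 0.005: 12% to 51%.

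For two equally good scores correlated 0.95, 0.91 and 0.83, the simulated paired SEs of 0.0045, 0.0062 and 0.0085 give half-widths (× 1.96) of 0.009, 0.012 and 0.017.

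**The case against.** The strongest reply is that nothing visible is shown to be unresolved. The only component gap in the text, 0.036, is at least twice the half-widths above. The other values sit in Table 2 and the supplements, which may carry intervals. That stands, and it limits the point to what the text plans and reports. Intervals for single models would still not be intervals for paired differences, and the missing method in sections 4 and 6 does not depend on those tables.

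A reader might infer several stronger things that the documents do not support:

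- **That 799 patients are too few to separate the models.** The RSF gap very probably would be separated. Limited power for very small gaps is true of any sample.
- **That the lead over the 12 systems is fragile.** The calculation for equally good, highly correlated scores suits ensemble components. Nothing shows that coarse staging systems lie within sampling error of PTA.
- **That there are 72 sign readings (18 × 4).** The text ranks the six algorithms on C-index; it sets IBS against the 0.25 threshold and does not compare three AUCs for them.
- **That CoxPH would serve as well if its interval included 0.** With 19% to 80% power at a gap of about 0.01, such an interval could hide a real gain. Nor would an equal C-index mean equal use: a Cox model without treatment interactions would favour the same treatment for everyone, and the terms of the fitted model are not shown.
- **That CoxPH should be the single primary comparator.** The documents give no basis for this, and the choice would be made after the results.

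**Conclusion.** The point holds in limited form. The text concludes superiority from rank order, with no planned or reported method for a paired difference against any of 18 comparators. The gap of 0.036 over RSF is very probably real in the sampling sense. Differences below about 0.02 may not be resolved, and the text does not show whether any of the other five component models lies that close. The conclusion that PTA outperformed all its components is therefore not established by what is printed; it is not shown to be false.

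The sizes rest on an assumed C-index SE of about 0.010 to 0.0125, on assumed correlations between models, and on a simulation whose PTA C-index was about 0.807 rather than the printed 0.801.

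**What to change.** On the validation patients, report PTA minus each comparator: the difference in C-index for all 18, and in the 1-, 3- and 5-year AUC where these are compared. Give each a 95% bootstrap interval, holding the fitted models fixed and resampling patients once for all models so that the pairing is kept. Add the method to section 6 and name the cohort used for each comparison.

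Say that PTA outperformed a comparator only where the interval excludes 0. Where it includes 0, say that no gain in discrimination was demonstrated, and do not call the models equivalent.

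The cost is a little extra analysis on existing predictions, with no new data. Some superiority statements may have to be softened.

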An ensemble model was developed and named the precise treatment allocation (PTA) model in our study. It could accurately predict the survival probability of each patient by alternating the different treatments. The inputs of the PTA model mainly comprise four modules: (a) liver function, such as serum albumin, serum bilirubin, and coagulative function indexes; (b) tumor burden, including serum alpha-fetoprotein (AFP), tumor size, and tumor number; (c) demographic data, such as age and gender; and (d) routine laboratory indications, such as routine blood examination and kidney function indexes. To further estimate the predictive performance of the PTA model, it was compared with other prognostic models, including widespread clinical guidelines (BCLC, BCLC B sub-classification ^[9], HKLC, and the most recent Italian Liver Cancer [ITA.LI.CA] staging system ^[10]), other tumor-burden-based models (up-to-seven model ^[11], four-and-seven model ^[12], and six-and-twelve model ^[13]), and models incorporating other parameters (hepatoma arterialembolization prognostic [HAP] score, modified HAP [mHAP] II score ^[13], mHAP III score ^[14], albumin-bilirubin [ALBI] score ^[15], and the model to estimate survival in ambulatory HCC patients [MESIAH] ^[16]), by estimating the auROC and C-index.

Here, HCC patients could achieve two potential survival rates and predicted median survival times (MSTs) by choosing TACE or LR. The ideal LR candidate is defined as a patient whose MST could be extended by more than 50% compared with the MST of primary treatment if LR is adopted in the model. Similarly, ideal TACE candidates are those with an additional survival benefit of more than 50% compared to LR allocation in TACE prediction time. Considering that BCLC and HKLC ^[17] have clearly defined LR and TACE candidates, the ideal LR and TACE candidates of the PTA model were compared with candidates recommended by these two widely used guidelines.

5. Web implementation

After train and validation, the optimized PTA model was implemented as a web

interface, which generates the MST and depict integrated survival curves composed of LR and TACE according to the clinic parameters of specific patients provided by users. Relative algorithms of web development were described in the supplement 1.

6. Statistical analyses

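### PTA, which uses the treatment received, is compared with 12 systems not described as using it, with no stated split by treatment, so an unknown part of its reported lead may come from knowing the treatment

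*Combined protocol and SAP*

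**What the plan says.** Section 4 (Model estimation) sets up the comparison: "To further estimate the predictive performance of the PTA model, it was compared with other prognostic models". The comparators are four guideline stagings (BCLC, BCLC B sub-classification, HKLC, ITA.LI.CA), three tumour-burden models (up-to-seven, four-and-seven, six-and-twelve) and five other scores (HAP, mHAP II, mHAP III, ALBI, MESIAH), 12 in all. The measures are auROC and C-index. No split by treatment is stated, and no step adds treatment to a comparator.

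The same section says that PTA predicts each patient's survival under either treatment by switching the treatment. Treatment is not among its four listed input modules, but that list is given as the main inputs only, and the results (Basic clinical characteristics) are explicit: "we perceived therapy type as a pivotal factor in the AI models".

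Under Predictive performance of the PTA model, PTA has undivided AUCs of 0.912, 0.914 and 0.928 at 1, 3 and 5 years. Treatment-specific values follow: "the AUCs for TACE treatment were 0.893" at 1 year, then 0.857 and 0.858; for LR they are 0.873, 0.850 and 0.839. The text gives such values for PTA only. The conclusion on the 12 systems is then undivided: "the 1-, 3- and 5-year auROC and C-index of the PTA model were higher than those of the above mentioned models and prognostic scores".

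**The concern.** The two sides of the comparison do not hold the same information. In any pair made up of one LR and one TACE patient, a model that knows the treatment has a strong prognostic fact that a stage or score lacks, before it reads anything about the patient. BCLC and HKLC define LR and TACE candidates, but that is a recommendation and not the treatment given.

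Some comparators also appear to be judged outside their setting. By their titles in the reference list, references 12 to 14 concern chemoembolization or arterial embolization, and references 9 and 12 concern BCLC B. About 38% of the cohort had LR.

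What is at stake is the superiority statement. It is offered in support of an individualized allocation tool, so readers will take it to mean that PTA reads patient characteristics better than the existing systems. A comparison in which only one side knows the treatment cannot separate that from the survival gap between treatments.

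**Working it through.** **Inputs.** Cohort: "1916 patients (38.39%) were amenable to LR while 3075 patients (61.61%) submitted to TACE" (1916/4991 = 38.39% and 3075/4991 = 61.61%, which agree). Validation set: "In validation set, 294 (36.8%) and 505 (63.2%) were allocated to LR and TACE treatment". Survival at 1, 3 and 5 years: "91.7%, 79.6%, and 70.8% for LR allocation" and "74.8%, 41.5%, and 26.4% for TACE treatment". The AUCs are those listed above. They cannot be regenerated without patient data, so what follows is a consistency check.

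**Assumptions.** The cohort's survival percentages apply in the validation set and can stand in for event status at each horizon.

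**Step 1: AUC of the treatment label alone.** Call every TACE patient a predicted death. Then AUC = (sensitivity + specificity)/2. At 5 years:
- Deaths: LR 294 × 0.292 = 85.8; TACE 505 × 0.736 = 371.7; total 457.5.
- Survivors: LR 294 × 0.708 = 208.2; TACE 505 × 0.264 = 133.3; total 341.5.
- Sensitivity 371.7/457.5 = 0.812; specificity 208.2/341.5 = 0.610; AUC = 0.711.

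The same steps give 0.628 at 1 year (0.839 and 0.416) and 0.679 at 3 years (0.831 and 0.528).

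**Step 2: share of dead–alive pairs that cross treatments.** At 5 years: LR–LR = 85.8 × 208.2/(457.5 × 341.5) = 0.114; TACE–TACE = 371.7 × 133.3/(457.5 × 341.5) = 0.317; the remainder, about 0.57, is cross-treatment. The shares at 1 and 3 years are 0.44 and 0.52.

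**Step 3: PTA's within-treatment AUC.** Weight the two treatment-specific AUCs by their within-treatment pairs. At 5 years: (0.114 × 0.839 + 0.317 × 0.858)/(0.114 + 0.317) = 0.853.

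| | 1 year | 3 years | 5 years |
|---|---|---|---|
| Treatment label alone, AUC | 0.628 | 0.679 | 0.711 |
| Cross-treatment pairs | 44% | 52% | 57% |
| PTA, undivided AUC | 0.912 | 0.914 | 0.928 |
| PTA, pair-weighted within treatment | 0.891 | 0.856 | 0.853 |
| Difference | 0.021 | 0.058 | 0.075 |

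With the whole-cohort mix the label AUCs are 0.631, 0.683 and 0.714 and the differences 0.022, 0.058 and 0.076, so the choice of mix hardly matters.

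**Step 4: what the label could be worth to a comparator (illustration).** Assume a normally distributed score that is independent of treatment given the outcome, with the whole-cohort mix. Adding treatment to a score with a within-treatment AUC between 0.60 and 0.80 raises its pooled AUC by 0.086 down to 0.026 at 1 year, 0.130 to 0.045 at 3 years and 0.156 to 0.058 at 5 years. The weaker the score, the larger the gain.

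**Which patients the AUCs come from.** The text does not say. The 1-year interval implies a standard error of (0.938 − 0.887)/3.92 = 0.013; the Hanley–McNeil formula gives 0.016 for 799 patients and 0.0065 for 4991. The validation set is the likelier source, by inference.

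**The case against.** Several points on the other side stand.

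- **No comparator value is available.** Table 2 is not in the text reviewed. The differences above are PTA pooled minus PTA within treatment, not PTA minus a comparator. That Table 2 pools the treatments is the natural reading, but it is not stated in words; Table 2 or Supplement 5 may hold treatment-specific results.
- **Case mix contributes.** LR patients had smaller tumours (median 4.60 against 6.30 cm), fewer lesions and less Child stage B (11.1% against 17.6%). A score blind to treatment but using tumour burden or liver function would also gain from pooling. The label alone orders about 79%, 85% and 87% of cross-treatment pairs correctly; PTA's figures imply about 0.94, 0.97 and 0.98, so its cross-treatment performance goes beyond the label.
- **Sampling error.** The 1-year within-treatment value of 0.891 lies inside the undivided interval (0.887–0.938). At 3 years the undivided interval overlaps both treatment-specific ones, and at 5 years it overlaps that for TACE. Only LR at 5 years is separate.
- **Censoring.** Median follow-up is 36.1 months for TACE and 54.0 for LR, and the handling of patients not followed to 5 years is not described. The 5-year pair shares are therefore approximate.
- **Treatment as an input is intended.** The tool works by switching it. Section 4 also plans, and the results report, a comparison with BCLC and HKLC candidates. The results make it within each treatment group, but by Kaplan–Meier curves and hazard ratios and for those two systems only.

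These points limit the size of the effect. They do not make the comparison like for like, and PTA's own treatment-specific AUCs do not settle it without matching values for the comparators.

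A reader might infer that PTA's superiority is an artefact that would vanish within treatments. The documents do not support that: PTA's within-treatment AUCs are 0.839 to 0.893, and nothing shows a ranking reversing.

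**Conclusion.** The concern holds in a limited form. As described, the comparison favours PTA, because treatment received is strongly prognostic in this cohort (label-only AUC about 0.63, 0.68 and 0.71) and only PTA is described as using it. An unknown part of the reported superiority may reflect this.

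The excess of about 0.02, 0.06 and 0.075 is tempting to read as PTA's unfair margin. It is not. It mixes the treatment label with case mix and rests on the two assumptions stated with the calculation. The imbalance concerns the 12 external systems only, since therapy type is described as a factor in the AI models generally. This should be corrected before the superiority statement is relied on, but no reported result has been shown to be wrong.

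**What to change.** 1. In the validation set, report auROC and C-index for PTA and each comparator within TACE and within LR separately, with confidence intervals for the differences.
2. If a pooled comparison is kept, also refit each comparator in the train set as score plus treatment and evaluate it in the validation set, so that both sides know the treatment.
3. Apply the systems whose cited titles limit them to chemoembolization or arterial embolization (references 12 to 14) within TACE, and those limited to BCLC B (references 9 and 12) within BCLC B. Check the citation for six-and-twelve first: it points to reference 13, whose title concerns the hepatoma arterial-embolization prognostic score.
4. Wherever the pooled AUCs appear, show PTA's treatment-specific AUCs alongside. State which patients they come from and whether Table 2 pools the treatments.
5. Limit the superiority statement to what the like-for-like comparison shows.

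This is re-analysis of existing data plus rewording. The cost is wider intervals (PTA's 1-year interval for LR is already 0.805–0.941, against 0.887–0.938 undivided; on the assumed survival, LR has only about 294 × 0.083 = 24 deaths by 1 year in the validation set) and possibly a smaller margin for PTA. Better discrimination within a treatment would still not, by itself, validate the allocation between treatments.
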